## 14 Efficacy Analyses

The following analyses will be performed based on the FAS/SAF by dose level (in increasing order) and summarized by study part, except when otherwise stated. In case a participant received  $> 120\%$  cumulative dose of the planned dose, the data of this participant will not be included in efficacy summary outputs. The data will be displayed in listings and figures but with a footnote stating the actual cumulative dose.

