At the discretion of the SMC, if the toxicity and tolerability profile of M4076 remains ambiguous at any DL, including the MTD or if additional PK/Pd data are felt necessary at any DL below the MTD, additional participants may be studied at that DL to better define the toxicity, tolerability, PK, and Pd. The study procedures for these additional participant(s)/cohort(s) will be the same as that specified for other study participants/cohorts.

This study part will also investigate the pharmacodynamics of M4076 as a secondary objective. Paired tumor biopsies (optional) and serial blood samples (mandatory) will be collected to evaluate markers of ATM inhibition.

If necessary, the Schedule of Activities will be adjusted, e.g. to ensure that PK and Pd samples are collected at the appropriate time points.

Once the MTD and/or RDE is determined in Part 1A, the RDE from Part 1A will be used for the food effect cohort in Part 1B.

Intraparticipant Dose Escalation: No intraparticipant dose escalation is allowed. However, upon declaration of safety and tolerability of the MTD or RDE by the SMC, participants who are still receiving ongoing study intervention at doses lower than the RDE may be switched to the RDE if participants have not experienced any treatment-emergent related AEs greater than Grade 1.

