9.4.1 Efficacy Analyses

All efficacy analyses will be performed on the Full Analysis Set population unless otherwise specified (Table 16).

Table 16 Part 1A Efficacy Analyses

Endpoint	Statistical Analysis Methods
Part 1A	
Primary	No primary efficacy endpoint is specified.
Secondary	
Objective response according to RECIST 1.1 assessed by Investigator	
ORR will be determined as the proportion of participants with a confirmed objective response of PR or CR. Confirmation of the response according to RECIST 1.1 will be required no sooner than 4 weeks after the initial documentation of CR or PR.
 
The number and proportion of overall response (defined as CR + PR) will be tabulated.
 
The 95% CI for the ORR will be calculated using the Clopper-Pearson method.

DoR according to RECIST 1.1 assessed by Investigator	
DoR is defined as the time (months) from first documentation of objective response (CR or PR) to the date of first documentation of PD or death due to any cause, whichever occurs first.
 
Duration of response data will be censored on the date of the last non-missing tumor assessment for participants who do not have an event (PD or death) or for participants for which the event is reported after two or more missed subsequent scheduled tumor assessments.
 
Participants who do not have a baseline tumor assessment or who do not have any post baseline tumor assessments will be censored at the date of the start of study intervention.
 
Kaplan-Meier estimates (product-limit estimates) will be presented for the analysis of DoR together with a summary of associated statistics (median DoR and response rate estimates at 3, 6, 12 months and every 6 months thereafter if applicable) including the corresponding 2-sided 95% CIs.

PFS according to RECIST 1.1 assessed by Investigator	PFS is defined as the time (in months) from date of first administration of study intervention to the date of the first documentation of PD or death due to any cause, whichever occurs first. The censoring rules for PFS are as described above for DoR. Kaplan-Meier estimates (product-limit estimates) will be presented for the analysis of PFS together with a summary of associated statistics (median PFS time and PFS rate estimates at 3, 6, 12 months and every 6 months thereafter if applicable) including the corresponding 2-sided 95% CIs.
Tertiary/Exploratory	Will be specified in the Integrated Analysis Plan, finalized before database lock.

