### Definition of actual dose

Unless otherwise specified, analyses of safety, efficacy and PK parameters will be conducted by actual dose. In this open label, unblinded study, actual dose is determined by considering study drug compliance during the DLT evaluation period (first 21 days from first dose of M4076) and whether the subject experienced a DLT (as per SMC determination). If a different regimen is tested, all subjects remain in the regimen to which they were assigned (i.e. subjects cannot be assigned to a different pre-specified dose level with a different dosing scheme).

In this context, compliance is defined as the cumulative actual dose taken by the subject divided by the cumulative cohort-level planned dose the subject was expected to receive. The planned dose level will be taken from the electronic case report form (eCRF) “Cohort”. The following table will be used to determine actual dose level:

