**Table 1 Actual Dose Assignment**

Compliance of planned dose	DLT Status	Compliance relative to other pre-specified dose levels	Actual dose
> 100%	Any	≥ 80% a higher pre-specified dose level	Higher pre-specified dose level
> 100%	Any	< 80% a higher pre-specified dose level (or no higher dose level)	Planned dose level
≤ 100%	DLT	Any	Planned dose level
≥ 80% and ≤ 100%	No DLT	Any	Planned dose level
< 80%	No DLT	≥ 80% of a lower pre-specified dose level	Lower pre-specified dose level
< 80%	No DLT	< 80% of the lowest pre-specified dose level (or no lower dose level)	Lowest received pre-specified dose level*

\*Patient is not evaluable for DLT analysis set

Note: In case a subject received >120% cumulative dose of the planned dose but ≤ 80% of the next higher pre-specified dose the data of this subject will not be considered in Pd and efficacy summary outputs. The data will be displayed in listings and line plots but with a footnote stating the actual cumulative dose.

In the event there are subjects whose 'actual' dose differs from the planned dose, disposition, compliance and exposure will be described by both planned and 'actual' dose.

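### SAP Section 14 drops every participant above 120% of planned cumulative dose from the efficacy summaries, in conflict with the narrower rule in SAP Section 9

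*SAP*

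**What the plan says.** **SAP Section 14 (Efficacy Analyses)** bases efficacy on the FAS/SAF, allowing for stated exceptions. It then says that once a participant is above 120% of the planned cumulative dose, "the data of this participant will not be included in efficacy summary outputs". The data stay in listings and figures with a footnote. No other condition and no period is given.

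**SAP Section 9 (Definition of actual dose, Table 1)** is narrower. Its note covers a subject above 120% of planned "but ≤ 80% of the next higher pre-specified dose the data of this subject will not be considered in Pd and efficacy summary outputs". A participant above 100% of planned and "≥ 80% a higher pre-specified dose level" is assigned to that higher level and stays in the analysis. Section 9 also sets a window: "actual dose is determined by considering study drug compliance during the DLT evaluation period (first 21 days from first dose of M4076".

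**SAP Section 13** defines cumulative dose as the total of all doses received over treatment. **SAP Section 8.1** puts every screened participant with at least one dose in the FAS/SAF. **SAP Section 7** declares no change from the protocol.

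**Protocol Section 9.4.1:** "All efficacy analyses will be performed on the Full Analysis Set population unless otherwise specified".

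**Protocol Section 4.1.1** bars intraparticipant escalation. The exception is that, after the RDE (or MTD) is declared, participants still on treatment below the RDE "may be switched to the RDE if participants have not experienced any treatment-emergent related AEs greater than Grade 1".

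**The concern.** Two parts of the SAP give different rules for the same participants. A programmer who follows Section 14 removes people whom Table 1 of Section 9 re-assigns and keeps.

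The missing time window raises a second question. If cumulative dose in Section 14 means the whole-treatment total of Section 13, a permitted switch up to the RDE raises the ratio of actual to planned dose and can carry it past 120%. Anyone who switches is, by construction, still on treatment when the RDE is declared. Exclusion would then depend on how long a participant stayed on treatment, which is related to outcome. The whole participant would go from the summaries, including a response confirmed before the switch. At the lower doses this could pull ORR, PFS and DoR downward. Since figures keep these participants, a waterfall or swimmer plot could show a responder who is absent from the ORR table.

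**Working it through.** The plan states no figure on this point, so there is none to reproduce. The check compares the two rules and then works out when a switch would cross 120%.

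**1. Where Section 9 excludes anyone.** Inputs: the 120% and 80% cut-offs (SAP Section 9) and the levels 100, 200, 300, 400 and 600 mg (protocol Section 4.1.1). The Section 9 zone runs from 120% of planned up to 0.8 × next level ÷ planned level.

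| Planned | Next | Upper edge (% of planned) | Section 9 excludes | Section 14 excludes |
|---|---|---|---|---|
| 100 mg | 200 mg | 0.8 × 200/100 = 160% | 120–160% | all above 120% |
| 200 mg | 300 mg | 0.8 × 300/200 = 120% | nobody | all above 120% |
| 300 mg | 400 mg | 0.8 × 400/300 = 106.7% | nobody | all above 120% |
| 400 mg | 600 mg | 0.8 × 600/400 = 120% | nobody | all above 120% |
| 600 mg | none | not defined | note has no next level | all above 120% |

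At 200, 300 and 400 mg, anyone above 120% is moved up a level by Table 1 but removed by Section 14. At 100 mg the rules differ above 160%. Protocol Section 9.4.2.1 and Appendix 12 omit 300 mg from their level lists. If 300 mg is not counted as pre-specified, the upper edge at 200 mg is 0.8 × 400/200 = 160%, so 200 mg also has a 120–160% zone. The conflict remains.

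**2. When a switch would cross 120%, on the whole-treatment reading.** Assumptions: daily dosing without missed doses or reductions, and planned dose held at the cohort level after the switch. For starting dose d, RDE R and share f of dosing time at R:

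actual ÷ planned = 1 + f(R/d − 1), which exceeds 1.2 when f > 0.2/(R/d − 1).

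| Switch | Share at RDE needed | Weeks at RDE after 6 weeks at d, 6f/(1 − f) |
|---|---|---|
| 100 to 200 mg | 20% | 1.5 |
| 100 to 300 mg | 10% | 0.67 |
| 100 to 400 mg | 6.7% | 0.43 |
| 100 to 600 mg | 4% | 0.25 |
| 200 to 300 mg | 40% | 4 |
| 200 to 400 mg | 20% | 1.5 |
| 300 to 400 mg | 60% | 9 |
| 400 to 600 mg | 40% | 4 |

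Examples with assumed durations:
- 100 mg for 63 days, then 200 mg for 21: (6,300 + 4,200)/8,400 = 125%, excluded.
- 100 mg for 84 days, then 300 mg for 42: (8,400 + 12,600)/12,600 = 167%, excluded.
- 200 mg for 84 days, then 400 mg for 42: (16,800 + 16,800)/25,200 = 133%, excluded.
- 300 mg for 63 days, then 400 mg for 21: (18,900 + 8,400)/25,200 = 108%, kept.

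**3. The same switch under Section 9's window.** Only the first 21 days count. Protocol Section 6.6.2.1 allows no dose modification in the Part 1A DLT period, so a switch after Day 21 excludes nobody.

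**4. Size of one loss (hypothetical).** Removing one responder, with Clopper-Pearson 95% intervals: 1/3 = 33.3% (0.8–90.6) becomes 0/2 = 0% (0–84.2); 1/6 = 16.7% (0.4–64.1) becomes 0/5 = 0% (0–52.2).

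**The case against.** The strongest reply is that Section 14 is a shortened restatement of the Section 9 note. It has the same 120% threshold, the same efficacy outputs and the same footnoted listings. On that reading the missing condition and window are drafting slips, and no switcher is affected. This is plausible and it makes the switcher effect conditional. It does not remove the conflict, because Section 14 neither refers to the note nor states a window, and the adjacent Section 13 defines cumulative dose over all treatment.

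A reader might infer that RDE switchers are routinely dropped. The documents do not support that. Switching is optional, limited to participants still on treatment without related events above Grade 1, and no expected number is given. Escalation is sequential with a 21-day DLT period, so low-dose participants would have to stay on through later cohorts. The protocol estimates about 105 days on study, and two of the examples above use 126 dosing days. Some steps need 40% or 60% of dosing time at the RDE. Nor do the documents say how planned dose is counted after a switch; if it is reset, the effect disappears.

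A reader might also infer a plain breach of the protocol's analysis set. That is too strong, since both protocol Section 9.4.1 and SAP Section 14 allow stated exceptions. It is fair to say only that the exclusion departs from the set of all dosed participants and that SAP Section 7 does not mention it.

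Finally, efficacy is secondary and descriptive, no hypothesis is tested, and the RDE rests on safety, PK and pharmacodynamic data. That limits the consequence and stands in full.

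**Conclusion.** Wrong as written, for secondary descriptive endpoints. The definite part is the rule conflict. Section 14 excludes everyone above 120% of planned at every level. Section 9 excludes only the 120–160% band at 100 mg and nobody at 200, 300 or 400 mg, or adds the same band at 200 mg if 300 mg is not counted as pre-specified. This holds even if nobody switches.

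The conditional part is the effect on switchers. It needs a switch to occur, the whole-treatment reading, planned dose held at the cohort level, and enough time at the RDE: from 4% (100 to 600 mg) to 60% (300 to 400 mg) of dosing time. Where these hold, removal is tied to staying on treatment and could bias lower-dose ORR, PFS and DoR downward. In cohorts of about 3, one lost responder decides whether the observed rate is 1/3 or 0/2, although neither estimate is precise.

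**What to change.** 1. Delete the Section 14 exclusion, so that all FAS participants stay in the efficacy summaries, and bring the Section 9 note into line. At minimum, give Section 14 the same second condition as the note and limit it to the first 21 days. If any exclusion is kept, list it in SAP Section 7, say what applies at the top dose level, and settle the case of exactly 80%, which currently falls under both Table 1 and the note.
2. State one dose-assignment rule for efficacy. The note to the analysis-set table in SAP Section 8.1 implies planned dose for efficacy, while Section 9 says actual dose.
3. Flag participants who switch to the RDE and commit to a sensitivity analysis of the efficacy endpoints censoring at the switch.

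The cost is SAP wording, one flag and one sensitivity output; trial conduct does not change. The downside is that, if switchers stay under their starting dose, a response first seen after the switch counts at that dose in the main table. The flag and the sensitivity analysis disclose this.

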### 14.1 Primary Estimand

No primary efficacy estimand is specified.

### 14.2 Further Estimands

No further estimands are specified.

#### 14.2.1 Secondary Endpoint: Objective Response (OR)

Tumor assessments are collected on the CRF pages: “Tumor Assessment - Target Lesions”, “Sum of Diameters”, “Tumor Assessment - Non-Target Lesions”, “Tumor Assessment - New Lesions” and “Assessment of Disease based on Imaging.”

**Best Overall response (BOR)** will be assessed based on reported overall responses at different evaluation time points from the study intervention start date until documented disease progression

in accordance to RECIST v1.1 by investigator, taking requirements for confirmation into account as detailed below.

Only tumor assessments performed before the start of any subsequent anti-cancer therapies will be considered in the assessment of BOR. If a tumor assessment was performed on the same day as start of new anti-cancer therapy, it will be assumed that the tumor assessment was performed prior to the start of the new anti-cancer therapy, therefore the tumor assessment will be included in the assessment of BOR.

Clinical deterioration will not be considered as documented disease progression. In the case of multiple dates of scans within the same tumor assessment, the earliest scan date will be used as the date of tumor assessment. The order to obtain the BOR is the following: CR, PR, SD, PD, NE. If a participant has no post-baseline tumor assessments before starting new anticancer therapy, BOR will be NE.

When SD is believed to be the best response, it must also occur after a minimum of 6 weeks from the start of study treatment. If the minimum time is not met, the participant's BOR depends on the subsequent assessments. For example, a participant who has SD at the first assessment, PD at the second assessment, and does not meet the minimum duration for SD, the BOR will be PD. If the same participant is lost to follow-up after the first SD assessment, BOR would be considered NE.

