1.3.1 Part 1A – M4076 Monotherapy Dose Escalation (Daily Dosing)

The schedule of events for Part 1A are provided in [Table 1](#).

The Part 1A fasting window is defined as: 2 hours predose to 1-hour postdose in general, and ~~C~~ hours predose to 4 hours postdose on days where PK-time matched triplicate ECGs are collected.

~~C~~
I

Table 1 Schedule of Activities: M4076 Monotherapy Dose Escalation (Daily Dosing), Part 1A

Assessments and Procedures	Screen (D -28 to -1)	DLT Period (21 days)					Subsequent 3-week Periods (21 days)			End of Study Intervention Visit	Safety Follow up/ Discontinuation Visit	Notes
Day		1	2	8	9	15	1	8	15	Within 7 days after last dose	30 days after last dose	
Visit Window (days)		-1								+7	+/- 7	Day 1 assessments that could be completed on Day -1 are limited to physical examination, height/weight, and ECOG performance status.
Study Site Visits	X	X	X	X	X	X	X	X	X	X	X	Starting Cycle 4, visits at Day 8 and Day 15 are optional
Written informed consent	X											
Inclusion / Exclusion Criteria	X											
Medical History (includes substance usage); Demography	X											Substances: tobacco use only.
Hepatitis B and C tests	X											To rule out active infection, performed at the Investigator's discretion. See Appendix 6 for details.
Optional HIV Screening	X											HIV testing is optional at the Investigator's discretion unless required locally.

Assessments and Procedures	Screen (D -28 to -1)	DLT Period (21 days)					Subsequent 3-week Periods (21 days)			End of Study Intervention Visit	Safety Follow up/ Discontinuation Visit	Notes
Day		1	2	8	9	15	1	8	15	Within 7 days after last dose	30 days after last dose	
Visit Window (days)		-1								+7	+/- 7	Day 1 assessments that could be completed on Day -1 are limited to physical examination, height/weight, and ECOG performance status.
Serum Pregnancy Test (WOCBP only)	X									X		See Section 8.3.5.
Urine Pregnancy Test (WOCBP only)		X				X						Urine β -hCG results must be available prior to M4076 dosing.
Physical Examination	X	X		X	X	X				X	X	See Section 8.2.1.
Height and Weight	X	X				X				X	X	Collect height at Screening only.
Imaging Disease Assessment (CT/MRI)	X	X (at the end of every 6 weeks for the first 24 weeks, then every 12 weeks)								X		Tumor assessment according to RECIST 1.1 until disease progression, end of study, or death, whichever is earlier. See Section 8.1 for details of imaging.

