8.1 Efficacy Assessments and Procedures

Radiographic images and physical findings (physical assessments) will be used by the Investigators for the local determination of disease progression and participant treatment decisions. Refer to the RECIST 1.1 publication for additional information ([Eisenhauer 2009](#)).

Whenever available, the longest diameter measurement of each target lesion and short axis for nodes derived from historical computerized tomography (CT)/magnetic resonance imaging (MRI) scans over a period of up to 100 days prior to enrollment should be collected in order to assess tumor growth dynamics prior to study enrollment. For comparability, target lesions in both historical and on-treatment scans should match, if possible. Participants will have a chest and abdominal imaging scan (e.g., computed tomography, magnetic resonance imaging) as appropriate and, if clinically indicated, imaging scans of other body areas (e.g., bone, pelvis). Participants should have a repeat imaging scan as described in the Schedule of Activities in [Section 1.3](#). All imaging scans to assess disease progression should be performed using similar imaging platforms and imaging techniques, including the use or absence of contrast, and should be of consistent anatomic locations with prior imaging scans, whenever possible. At End of Study Intervention visit, the tumor assessment should only be performed if no disease progression was previously documented.

Imaging scans will be locally read for all parts of the study. The applicable overall response category for each visit that includes disease assessment, based on evaluation of imaging scan, will be recorded in the CRF. Determination of participant study disposition (i.e., discontinuation or extension of therapy) will be based on disease progression as interpreted from the local evaluation of the imaging scan.

For assessment time points and procedures for primary, secondary, and tertiary/exploratory efficacy endpoints, see Schedule of Activities ([Section 1.3](#)).

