#### **BOR Based on Confirmed Responses:**

- Complete Response (CR) = at least two determinations of CR at least 4 weeks apart (with no PD in between)
- Partial Response (PR) = at least two determinations of PR or better (PR followed by PR or PR followed by CR) at least 4 weeks apart (and not qualifying for a CR), with no PD in between
- Stable Disease (SD) = at least one SD assessment (or better)  $\geq$  6 weeks after start date (and not qualifying for CR or PR).
- Non-CR/non-PD (applicable only to participants with non-measurable disease at baseline) = at least one non-CR/non-PD assessment (or better)  $\geq$  6 weeks after start date (and not qualifying for CR or PR).
- Progressive Disease (PD) = PD  $\leq$  12 weeks after start date of study treatment (and not qualifying for CR, PR, non-CR/non-PD or SD).
- Not Evaluable (NE): all other cases.

Confirmation of response is not necessarily required at the next scan, but could be at any subsequent scan before PD. For instance, if a participant has PR-SD-PR or PR-NE-PR at consecutive tumor assessments, the best overall response will qualify for PR.

SD can follow PR only in the rare case that tumor increases by less than 20% from the nadir, but enough that a previously documented 30% decrease from baseline no longer holds. If this occurs the sequence PR-SD-PR is considered a confirmed PR. A sequence of PR – SD – SD – PD would be a best response of SD if the minimum duration for SD definition has been met.

**Confirmed Objective Response (OR)** is defined as a confirmed best overall response of complete response (CR) or partial response (PR) according to RECIST v1.1.

Participants who do not have an on-treatment radiographic tumor assessment due to early progression, who receive anti-tumor treatments other than the study intervention prior to reaching confirmed CR or PR, or who die, progress, or drop out for any reason prior to reaching confirmed CR or PR will be counted as non-responders in the assessment of OR. Each participant will have an objective response status (0: 'no OR'; 1: 'OR').

OR rate (ORR) is the proportion of participants with OR in the analysis set. No formal statistical hypotheses will be tested.

The number and percentage of participants with unconfirmed and confirmed BOR of CR, PR, SD, on-CR/non-PD, PD, and NE will be tabulated.

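### The 6-week minimum for stable disease and the 12-week limit for progression fall exactly on the first two scheduled scans, with no tolerance, and the SAP's two statements of the rule disagree for progression found after week 12

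*SAP*

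**What the plan says.** SAP 14.2.1 states the rule twice. The narrative says that for SD to be the best response "it must also occur after a minimum of 6 weeks from the start of study treatment", and continues: "If the minimum time is not met, the participant's BOR depends on the subsequent assessments". It gives two examples: early SD followed by PD is PD, and early SD followed by loss to follow-up is NE. The first example carries no time limit on the PD.

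The list headed BOR Based on Confirmed Responses then requires an SD-or-better assessment at 6 weeks or more after the start date. It sets the same minimum for non-CR/non-PD, accepts PD as BOR only if found within 12 weeks, and sends every remaining case to NE.

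Protocol Table 1 (Section 1.3.1) schedules imaging "at the end of every 6 weeks for the first 24 weeks, then every 12 weeks". Its visit windows are:

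- one day before Day 1, with the note that "Day 1 assessments that could be completed on Day -1 are limited to physical examination, height/weight, and ECOG performance status";
- +7 days for the End of Study Intervention Visit;
- ±7 days for safety follow-up.

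Protocol 8.1 adds nothing on timing: "Participants should have a repeat imaging scan as described in the Schedule of Activities".

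**The concern.** Each cut-off sits on the nominal date of a scan, so there is no margin on either side. Real scan dates move by a few days for reasons unrelated to the tumour. When the first scan slips earlier, or the second slips later, the reported category can change although the images would read the same.

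BOR is tabulated, shown on the swimmer plot and annotated on the waterfall plot, and efficacy is summarised by dose level. With planned cohorts of 3, a single reclassified participant is visible. The 12-week limit adds a second problem: a participant with two readable scans and documented progression can be labelled not evaluable, or not, depending on which part of the same SAP section the programmer follows.

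**Working it through.** No power or sample-size figure is involved. The check applies the SD, PD and NE rules to sequences of scan days.

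**Inputs**

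- 1 week = 7 days (SAP 9.4), so 6 weeks = 6 × 7 = 42 days and 12 weeks = 12 × 7 = 84 days.
- Day 1 is the first dose and there is no Day 0 (SAP 9.3, Part 1A).
- Durations are stop date minus start date plus 1 unless otherwise specified (SAP 9.3). A scan on Day d then counts as d days. Counting elapsed days instead gives d − 1.
- Scheduled scans: end of week 6 (Day 42) and end of week 12 (Day 84).

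**Rules as in the definition list**

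- SD if any scan reading SD or better has a count of at least 42.
- Otherwise PD if progression has a count of at most 84.
- Otherwise NE.

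**Results**

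| First scan | What follows | List, +1 count | List, elapsed days | Narrative examples |
|---|---|---|---|---|
| SD Day 41 | PD Day 84 | PD | PD | PD |
| SD Day 41 | PD Day 85 | NE | PD | PD |
| SD Day 41 | PD Day 86 | NE | NE | PD |
| SD Day 41 | no further scan | NE | NE | NE |
| SD Day 41 | SD Day 84, PD Day 126 | SD | SD | SD |
| SD Day 42 | PD Day 84 | SD | PD | as list |
| SD Day 43 | PD Day 84 | SD | SD | SD |

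**Reading the table**

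1. Under the SAP's default +1 count, a Day 42 scan just passes (42 ≥ 42) and a Day 41 scan fails (41 < 42). The margin is zero days.
2. An early first scan changes BOR only if no later scan at 6 weeks or more shows SD or better. That happens if the next scan shows PD, if there is no next scan, or if new anticancer therapy starts first.
3. For SD on Day 41 and PD on Day 86, the narrative gives PD and the list gives NE under either day count.
4. Two SAP date rules can only move scans earlier: the earliest date is used when an evaluation spans several days (14.2.1), and the 1st of the month is used when no scan day is recorded (9.8).

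**Size of one change.** In a planned cohort of 3 (Protocol 1.2), 1/3 = 33 percentage points. At the minimum of 6 for the MTD or RDE level, 1/6 = 17 percentage points.

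**The case against.** The strongest defence is that the SAP follows the protocol's own criteria. Protocol Appendix 9 contains the same rule and essentially the same example: SD, then PD, with the minimum not met, is a best response of PD. It describes the minimum SD interval as in general not less than 6 to 8 weeks, and 6 weeks is the bottom of that range. On this view the participant is not misclassified; the SD was simply too short to count. The effect is also narrow. The named activity endpoints are OR, DoR and PFS, none of which uses the SD minimum. The study is exploratory with no formal hypothesis test, and imaging dates are listed per participant, so an early scan can be seen.

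Most of this stands and limits the point to a refinement. It does not remove it. The same appendix leaves the SD interval, and the conditions for early progression and inevaluability, to be set for each study. Nothing in it requires the interval to coincide with the scan date without any margin. Nor does it resolve the conflict between the SAP's example and its definition list.

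A reader might infer more than the documents support, in three ways:

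- **That any first scan one day early turns SD into PD or NE.** It does not; a participant with SD or better at the week-12 scan keeps SD.
- **That an on-time Day 42 scan fails.** It fails only if elapsed days are counted, and the SAP's default is the +1 convention.
- **That a large share of SD results would be lost.** The documents give no distribution of scan dates. A share based on an assumed spread would count early scans, not changed categories.

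**Conclusion.** The point holds as a low-cost improvement. Both limits coincide with scheduled scans and no tolerance is given. A participant whose only SD falls at a slightly early first scan, with no later SD or better, is therefore reported as PD or NE. If progression is then found just past 12 weeks, SAP 14.2.1 supports two different answers, one of which is NE despite documented progression.

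The impact is confined to the SD, non-CR/non-PD, PD and NE rows of the BOR table and the BOR labels on the plots. Confirmed ORR, DoR and PFS are unaffected, and no disease control rate is defined in the visible text. The conclusion assumes that 6 and 12 weeks mean 42 and 84 days under the +1 convention, and that no imaging window is set in a document outside these two. How many participants would be affected is unknown.

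**What to change.** 1. State an imaging window of w days for on-treatment scans in Protocol Table 1 or Section 8.1. If the protocol is not amended again, put the tolerance in the SAP before database lock.
2. In SAP 14.2.1, write the SD and non-CR/non-PD minimum as 42 − w days and the PD limit as 84 + w days, both with the +1 convention spelled out. Keep w small and justify it against the 6-to-8-week guidance in Protocol Appendix 9. Purely to show the arithmetic, w = 1 would admit SD on Day 41 (41 ≥ 41) and PD on Day 85 (85 ≤ 85).
3. Reconcile the narrative example with the definition list, so that early SD followed by PD after the limit has one stated result.
4. Name the start date for the count in Part 1B, where the first single dose is on Day −7 but SAP 9.3 calls Day 1 the start of study intervention.

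The cost is a few lines in SAP 14.2.1 and one note in the protocol. The only downside is that a few slightly early scans will count as SD, so the SD rate may be marginally higher.
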